2.3.5 New Lesions

The appearance of new malignant lesions denotes disease progression; therefore, some comments on detection of new lesions are important. There are no specific criteria for the identification of new radiographic lesions; however, the finding of a new lesion should be unequivocal, that is, not attributable to differences in scanning technique, change in imaging modality, or findings thought to represent something other than tumor (eg, some “new” bone lesions may be simply healing or flare of preexisting lesions). This is particularly important when the patient’s baseline lesions show partial or CR. For example, necrosis of a liver lesion may be reported on a CT scan report as a “new” cystic lesion, which it is not.

A lesion identified during the study in an anatomical location that was not scanned at baseline is considered a new lesion and will indicate disease progression.

If a new lesion is equivocal, for example, because of its small size, continued therapy and follow-up evaluation will clarify if it represents truly new disease. If repeat scans confirm that there is definitely a new lesion, then progression should be declared using the date of the initial scan.

¹⁸F-Fluorodeoxyglucose Positron Emission Tomography

While ¹⁸F-fluorodeoxyglucose (FDG) PET response assessments need additional study, it is sometimes reasonable to incorporate the use of FDG-PET scanning to complement CT scanning in assessment of progression (particularly, possible “new” disease). New lesions on the basis of FDG-PET imaging can be identified according to the following algorithm:

A negative FDG-PET scan at baseline with a positive FDG-PET scan during the study is a sign of PD based on a new lesion.

In the case of no FDG-PET scan at baseline and a positive FDG-PET scan during the study:

- If the positive FDG-PET scan during the study corresponds to a new site of disease confirmed by CT, this will be considered PD.
- If the positive FDG-PET scan during the study is not confirmed as a new site of disease on CT, additional follow-up CT scans are needed to determine whether there is truly progression occurring at that site (if so, the date of PD will be the date of the initial abnormal FDG-PET scan).
- If the positive FDG-PET scan during the study corresponds to a preexisting site of disease on CT that is not progressing on the basis of the anatomic images, this will not be considered PD.

2.4 Evaluation of Response

2.4.1 Time Point Response (Overall Response)

It is assumed that, at each protocol-specified time point, a response assessment occurs. Table 13 provides a summary of the overall response status calculation at each time point for patients who have measurable disease at baseline.

When patients have non-measurable (therefore non-target) disease only, Table 14 is to be used.

Table 13 Time Point Response: Patients with Target Lesions (with or without Non-Target Lesions)

Target Lesions	Non-Target Lesions	New Lesions	Overall Response
CR	CR	No	CR
CR	Non-CR/non-PD	No	PR
CR	Not evaluated	No	PR
PR	Non-PD or not all evaluated	No	PR
SD	Non-PD or not all evaluated	No	SD
Not all evaluated	Non-PD	No	NE
PD	Any	Yes or no	PD
Any	PD	Yes or no	PD
Any	Any	Yes	PD

CR = complete response; NE = not evaluable; PD = progressive disease; PR = partial response; SD = stable disease.

Table 14 Time Point Response: Patients with Non-Target Lesions Only

Non-Target Lesions	New Lesions	Overall Response
CR	No	CR
Non-CR/non-PD	No	Non-CR/non-PD ^a
Not all evaluated	No	NE
Unequivocal PD	Yes or no	PD
Any	Yes	PD

CR = complete response; NE = not evaluable; PD = progressive disease.

^a “Non-CR/non-PD” is preferred over “stable disease” for non-target disease since stable disease is increasingly used as an endpoint for assessment of efficacy in some trials; thus, assigning “stable disease” when no lesions can be measured is not advised.

2.4.2 Missing Assessments and Not Evaluable Designation

When no imaging/measurement is done at all at a particular time point, the patient is not evaluable at that time point. If only a subset of lesion measurements are made at an assessment, usually, the case is also considered not evaluable at that time point, unless a convincing argument can be made that the contribution of the individual missing lesion(s) would not change the assigned time point response. This would be most likely to happen in the case of PD. For

example, if a patient had a baseline sum of 50 mm with 3 measured lesions and, during the study, only 2 lesions were assessed, but those gave a sum of 80 mm, the patient will have achieved PD status, regardless of the contribution of the missing lesion.

If one or more target lesions were not assessed either because the scan was not done or the scan could not be assessed because of poor image quality or obstructed view, the response for target lesions should be Not Evaluable (NE), unless the sum of the diameters of the remaining target lesions which were assessed is greater than 20% from nadir, in which case target lesion response should be PD. Similarly, if one or more non-target lesions are not assessed, the response for non-target lesions should be NE, except where there is clear progression for the remaining non-target lesions which were assessed. Overall response would be NE if either the target response or the non-target response is NE except where this is clear evidence of progression.

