6.1.13 Tumor Assessment

Tumor time point response assessment will be performed by the investigators according to RECIST Version 1.1 ([Appendix 8](#)) or RANO criteria for glioma subjects ([Appendix 9](#)). The tumor assessments will be performed during screening, every 8 weeks (± 1 week) beginning on C1D1 for the first 24 weeks, and every 12 weeks (± 2 weeks) thereafter as specified in [Table 1](#) and [Table 2](#), through EOT or end of Efficacy Follow-up (if applicable).

All measurable and evaluable lesions should be assessed and documented using image-based evaluation. All subjects are to be evaluated utilizing contrast-enhanced computed tomography (CT) scan or positron emission tomography (PET) scan or Gd MRI for glioma subjects to identify and follow selected lesions throughout the study. In addition, other radiographic or scintigraphic procedures (such as radionuclide bone scans), as deemed appropriate by the investigator, will be performed to assess sites of neoplastic involvement.

Tumor assessments completed as standard of care prior to signing of the informed consent but, within 28 days of first dose of study treatment, may be used as baseline scans. Assessments throughout the study should be made using the same modality as used at Screening.

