9.2.7 Efficacy Analysis

The investigator shall evaluate efficacy according to the corresponding criteria for all subjects according to RECIST Version 1.1 (RANO criteria for glioma subjects).

Efficacy evaluation indicators include ORR, DCR, DoR, TTR, PFS, and OS.

- ORR: Defined as the proportion of subjects achieving a best overall response of confirmed complete response (CR) or partial response (PR)
- DCR: Defined as the proportion of subjects achieving a best overall response of confirmed CR, PR, or stable disease (SD)
- DoR: Defined as the time from the first occurrence of PR or CR, whichever comes first until disease progression or death
- TTR: Defined as the time from the start of study treatment to the first occurrence of objective response (PR or CR, whichever comes first)
- PFS: Defined as the time (months) from the start of study treatment until the first radiographic documentation of objective progression as assessed by the investigator using RECIST Version 1.1 or death from any cause
- OS: Defined as the time from the start of the study drug until death from any cause

The estimate of ORR and DCR and the corresponding 95% CI will be presented by tumor type. For time-to-event endpoints such as PFS, TTR, DoR, and OS, the medians and rates at various time points along with 95% CI will be estimated by Kaplan-Meier methodology.

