4.2.1.2. Objective Response Rate, and Disease Control Rate

Objective response rate (ORR) by RECIST will be calculated using two different ways:

- Scenario #1: ORR will be calculated using a strict interpretation of RECIST Version 1.1. Objective response will be derived as no/yes variable. Patients with a BOR of confirmed CR or PR will be assigned ‘Yes’. Patients not having a BOR of confirmed CR or PR will be assigned ‘No’. Hence, ORR is defined as the proportion of patients with confirmed objective response being “Yes”.
- Scenario #2: ORR_{UNCONFIRMED} will be calculated using all responses regardless of confirmation. Objective response will be derived as no/yes variable. Patients with a BOR of confirmed CR, confirmed PR, unconfirmed CR or unconfirmed PR will be assigned “Yes”. All patients with other BOR values will be assigned “No”. Hence, ORR_{UNCONFIRMED} is defined as the proportion of patients with unconfirmed objective response being “Yes”.

Both ways (confirmed and unconfirmed) of assigning BOR will be implemented.

ORR defined as the proportion of patients with a confirmed BOR of complete response (CR) or partial response (PR) as determined by the investigator using RECIST v1.1.

ORR by RANO is defined as the proportion of patients with a BOR of complete response (CR) or partial response (PR) or MR as determined by the investigator using RANO.

Disease control rate (DCR) by RECIST is defined as the proportion of patients with a BOR of CR, PR, or SD lasting at least 7 weeks as determined by the investigator using RECIST v1.1.

DCR by RANO is defined as the proportion of patients with a BOR of CR, PR, MR, or SD lasting at least 7 weeks as determined by the investigator using RANO criteria for glioma patients.

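### Appendix 8 gives two incompatible overall responses for RECIST patients with target lesions when non-target lesions are not all assessed, and neither document says which prevails

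*Protocol*

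**What the plan says.** Protocol Section 6.1.13 gives the reading to the sites: "Tumor time point response assessment will be performed by the investigators according to RECIST Version 1.1", or by RANO for glioma. The RECIST text is in Appendix 8.

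Appendix 8, Section 2.4.1, states the scope of the first rule: "Table 13 provides a summary of the overall response status calculation at each time point for patients who have measurable disease at baseline". In that table, target PR or target SD combined with non-target lesions described as "Non-PD or not all evaluated", and no new lesion, gives PR or SD respectively. Target CR with non-target lesions not evaluated gives PR.

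Appendix 8, Section 2.4.2, gives the second rule in two steps. First, "if one or more non-target lesions are not assessed, the response for non-target lesions should be NE", with clear progression as the only exception. Second, "Overall response would be NE if either the target response or the non-target response is NE except where this is clear evidence of progression". An earlier sentence in the same section is softer. It says that a visit with only a subset of lesions measured is usually not evaluable, "unless a convincing argument can be made that the contribution of the individual missing lesion(s) would not change the assigned time point response".

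SAP Section 4.2.1.2 says of the confirmed analysis: "ORR will be calculated using a strict interpretation of RECIST Version 1.1". The SAP builds best overall response, ORR, DCR, DoR, TTR and PFS on the time-point responses. It has no rule for combining target and non-target results. The notes to SAP Tables 3 and 5 count an assessment as adequate only if the investigator's response is CR, PR, SD or PD, so NE is not adequate.

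**The concern.** A patient whose target lesions were fully measured can be recorded as PR or as NE, depending on which part of Appendix 8 the site reads. The SAP's strict interpretation does not settle this, because the protocol's own version of the criteria contains both answers. The situation is foreseeable: Section 2.5 of the same appendix lets some non-target organs be imaged less often than the target lesions.

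At stake is whether best overall response, DCR, DoR and PFS are comparable between sites. The SAP reports efficacy by dose level and disease type in an escalation part of about 27 to 36 subjects, so one reclassified patient is visible in a group.

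**Working it through.** There is no stated figure to reproduce. The check sets the two rules side by side and runs both results through the SAP.

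**Step 1. The two rules (no new lesion, no progression).**

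| Target | Non-target | Table 13 | Section 2.4.2 |
|---|---|---|---|
| CR | not evaluated | PR | NE |
| PR | not all evaluated | PR | NE |
| SD | not all evaluated | SD | NE |

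All three rows differ. Where target lesions are missing, both rules give NE. Where the patient has non-target disease only, Table 14 and Section 2.4.2 also agree on NE.

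**Step 2. Inputs for the consequences.**
- Scans every 8 weeks to week 24, then every 12 weeks (Protocol 6.1.13). With C1D1 as day 1 the nominal days are 57, 113, 169, 253 and 337.
- Confirmation needs at least 4 weeks, and one intervening NE or SD is allowed. SD as best response needs 49 days on study (SAP 4.2.1.1, Table 2 and notes).
- Progression after a long gap is censored at the last adequate scan. The gap limit is 126 days if that scan is before day 120, 161 days from day 120 to day 176, and 196 days after that (SAP 4.2.1.3).
- Time in months = (date − start + 1)/30.4375, which for study day d is d/30.4375.

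**Step 3. Illustrative sequences (not trial data).** "Missed" below means target lesions measured and a non-target lesion not assessed.

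| Case | Table 13 | Section 2.4.2 |
|---|---|---|
| 1. PR wk 8; target PR, missed wk 16; PD wk 24 | PR-PR-PD: confirmed PR; PFS event day 169 (5.6 mo) | PR-NE-PD: SD, since 57 > 49; gap 169 − 57 = 112 < 126, so the same PFS event |
| 2. Target SD, missed wk 8; PD wk 16 | SD-PD: SD, counted in DCR | NE-PD: PD, not counted |
| 3. SD wk 8; target SD, missed wk 16; data cut-off | Censored day 113 (3.7 mo) | Censored day 57 (1.9 mo) |
| 4. SD wk 8 and 16; target SD, missed wk 24; PD wk 36 | Event day 253 (8.3 mo) | Gap 253 − 113 = 140 ≥ 126: censored day 113 (3.7 mo) |
| 5. SD to wk 24; target SD, missed wk 36; PD wk 48 | Event day 337 (11.1 mo) | Gap 337 − 169 = 168 ≥ 161: censored day 169 (5.6 mo) |
| 6. PR wk 8; target PR, missed wk 16 and 24; PD wk 36 | Confirmed PR; DoR (253 − 57 + 1)/30.4375 = 6.5 mo; PFS event 8.3 mo | PR-NE-NE-PD: SD, no DoR; gap 253 − 57 = 196 ≥ 126: censored day 57 (1.9 mo) |
| 7. PR wk 8; target PR, missed wk 16; PR wk 24 | Confirmed PR | PR-NE-PR: confirmed PR, no change |

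Cases 4 and 5 show that one NE visit is enough where the gap spans 12-week scanning but the limit is set by an earlier scan. Once the last adequate scan is past day 176, one NE visit gives a gap of 2 × 84 = 168 days, below 196, so two are needed.

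**Step 4. Size in a group.** One reclassified patient moves a response or disease control rate by 100/n points. The documents do not give n for each reporting group. For an assumed n from 3 to 10 the shift runs from 33 down to 10 points.

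**The case against.** The best reply is that Section 2.4.2 leaves discretion: such visits are only usually not evaluable, and a convincing argument can rescue them. That does not reconcile the texts. The discretion is case by case and is no rule of precedence, and the explicit non-target sentence after it excepts only progression.

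A second reply is that a bone scan not repeated is no missed assessment, because Section 2.5 permits it. This is a fair reading and narrows the exposure. But Section 2.4.2 does not refer to that permission, so a site can still record NE.

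Several stronger readings are tempting, and the documents do not support them:
- A reader might infer that every affected visit moves the PFS or DoR date. Censoring moves back only if the NE visit is the last scan before censoring, and a progression is lost only if the gap limit is met. Case 1 leaves PFS unchanged.
- A reader might infer that an NE visit always defeats confirmation. One intervening NE is allowed (case 7). The SAP also reports ORR regardless of confirmation, where case 1 still counts as an unconfirmed PR. That protection fails only if the first response itself falls on the affected visit.
- A reader might infer that all efficacy data are affected. Glioma patients are assessed by RANO (Appendix 9), and Table 14 agrees with Section 2.4.2 for non-target-only disease.
- A reader might call the two rules opposite. PR or SD against NE is incompatible, not opposite.

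It also stands that these endpoints are secondary and descriptive, with no hypothesis test, and that per-patient tumor listings and target-lesion plots would let a careful reader notice a reclassification. Finally, the SAP is written to Protocol Amendment 3, while the protocol reviewed here is Amendment 2. Whether Appendix 8 changed in between is unknown.

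**Conclusion.** The point holds for RECIST patients with target lesions. In the current text three target and non-target combinations have two different overall responses, and nothing in either document chooses between them. Depending on the sequence, the same scans give a confirmed PR or SD, SD or PD, a censoring date one visit (8 or 12 weeks) earlier, or a PFS event turned into a censoring. Two consecutive NE visits can do the last, and so can one around the change to 12-week scanning.

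Severity is moderate. A reader might take this as a threat to the trial's main conclusions. It is not: the MTD, RP2D and safety endpoints do not use these responses, and no error rate or power is involved. Nor do the documents show how often non-target lesions went unassessed, or that any patient was reclassified. The worked cases assume nominal scan days, and the link to the SAP assumes that Appendix 8 is unchanged in Amendment 3.

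**What to change.** **Protocol Appendix 8, Section 2.4.2.** State that for patients with target lesions Table 13 governs the overall response: incomplete non-target assessment reduces a CR to PR but does not turn a measured PR or SD into NE. Keep the NE rule for missing target lesions and for non-target-only disease. Removing the non-target clause altogether would contradict Table 14, and Part 1 admits patients with evaluable but not measurable disease, who count for PFS.

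**SAP, before database lock.** Keep the investigator's response as the source. Check each NE time point against the recorded target, non-target and new-lesion responses using Table 13, and query discrepancies. Report BOR, ORR, DCR, DoR and PFS with the Table 13-consistent response where the components are recorded.

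**Cost.** A short clarification, a small amount of data review and some programming. It depends on the component responses being captured in the eCRF, which the documents supplied do not include. A site memo alone would not correct responses already entered.

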2.4.3 Best Overall Response: All Time points

The best overall response is determined once all the data for the patient are known. Best response determination in trials where confirmation of CR or PR **is not** required: Best response in these trials is defined as the best response across all time points (eg, a patient who has SD at first assessment, PR at second assessment, and PD on last assessment has a best overall response of PR). When SD is believed to be the best response, it must also meet the protocol-specified minimum time from baseline. If the minimum time is not met when SD is otherwise the best time point response, the patient's best response depends on the subsequent assessments. For example, a patient who has SD at first assessment and PD at second assessment and does not meet minimum duration for SD will have a best response of PD. The same patient lost to follow-up after the first SD assessment would be considered not evaluable.

Best response determination in trials where confirmation of CR or PR **is** required: CRs or PRs may be claimed only if the criteria for each are met at a subsequent time point as specified in the protocol (generally 4 weeks later). In this circumstance, the best overall response can be interpreted as in [Table 15](#).

Table 15 Best Overall Response When Confirmation of Complete Response and Partial Response is Required

Overall Response First Time point	Overall Response Subsequent Time point	Best Overall Response
CR	CR	CR
CR	PR	SD, PD, or PR ^a
CR	SD	SD provided minimum criteria for SD duration met; otherwise, PD
CR	PD	SD provided minimum criteria for SD duration met; otherwise, PD
CR	NE	SD provided minimum criteria for SD duration met; otherwise, NE
PR	CR	PR
PR	PR	PR
PR	SD	SD

Table 15 Best Overall Response When Confirmation of Complete Response and Partial Response is Required

Overall Response First Time point	Overall Response Subsequent Time point	Best Overall Response
PR	PD	SD provided minimum criteria for SD duration met; otherwise, PD
PR	NE	SD provided minimum criteria for SD duration met; otherwise NE
NE	NE	NE

CR = complete response; NE = not evaluable; PD = progressive disease; PR = partial response; SD = stable disease.

2.5 Frequency of Tumor Re-evaluation

Frequency of tumor re-evaluation while on treatment should be protocol specific and should be adapted to the type and schedule of treatment. However, in the context of phase 2 studies where the beneficial effect of therapy is not known, a follow-up every 6 to 8 weeks (timed to coincide

with the end of a cycle) is reasonable. Smaller or greater time intervals than these could be justified in specific regimens or circumstances. The protocol should specify which organ sites are to be evaluated at baseline (usually those most likely to be involved with metastatic disease for the tumor type under study) and how often evaluations are repeated. Normally, all target and non-target sites are evaluated at each assessment. In selected circumstances, certain nontarget organs may be evaluated less frequently. For example, bone scans may need to be repeated only when CR is identified in target disease or when progression in the bone is suspected.

After the end of the treatment, the need for repetitive tumor evaluations depends on whether the trial has as a goal the response rate or the time to an event (progression/death). If the “time to an event” (eg, time to progression, disease-free survival, and progression-free survival) is the main endpoint of the study, then routine scheduled re-evaluation of protocol-specified sites of disease is warranted. In randomized comparative trials in particular, the scheduled assessments should be performed as identified on a calendar schedule (eg, every 6 to 8 weeks on treatment or every 3 to 4 months after treatment) and should not be affected by delays in therapy, drug holidays, or any other events that might lead to imbalance in a treatment arm in the timing of disease assessment.

2.6 Confirmatory Measurement/Duration of Response

2.6.1. Confirmation

In non-randomized trials where response is the primary endpoint, confirmation of PR and CR is required to ensure that responses identified are not the result of measurement error. This will also permit appropriate interpretation of results in the context of historical data where response has traditionally required confirmation in such trials. However, in all other circumstances, for example, in randomized trials (phase 2 or 3) or in studies where SD or PD are the primary endpoints, confirmation of response is not required since it will not add value to the interpretation of trial results. However, elimination of the requirement for response confirmation may increase the importance of central review to protect against bias, particularly in studies that are not blinded.

In the case of SD, measurements must have met the SD criteria at least once after study entry at a minimum interval (in general, not less than 6 to 8 weeks) that is defined in the study protocol.

